1.2.2.2 Study WO42312

Study WO42312 (acelERA Breast Cancer) is a Phase II, randomized, open-label multicenter study evaluating the efficacy and safety of giredestrant compared with

physician's choice of endocrine monotherapy (PCET [fulvestrant or an aromatase inhibitor]) in patients with ER-positive, HER2-negative mBC who have received one or two prior lines of systemic therapy in the locally advanced or metastatic setting.

As of the CCOD (18 February 2022) for the primary analysis, of the 303 patients enrolled, 15.2% patients had discontinued from the study and the majority of those remaining had discontinued treatment; median duration of follow-up was 7.89 months.

Study WO42312 did not meet its primary endpoint of investigator-assessed PFS. Giredestrant showed a numerical improvement relative to physician's choice of endocrine therapy (PCET) in terms of PFS hazard ratio of 0.81 (95% CI: 0.60 to 1.10), which was not statistically significant ($p=0.1757$). Median PFS was similar between both arms: 5.55 months (95% CI: 4.93 to 7.36) with giredestrant and 5.36 months (95% CI: 3.71 to 5.55) with PCET and PFS benefit was more pronounced in the subset of patients with baseline ESR1 mutations (hazard ratio: 0.60 [95% CI: 0.35 to 1.03]). The OS data were still immature (<10% events). Numerical increases in other secondary endpoints were observed with giredestrant, for both CBR (31.8% vs. 21.1%) and ORR (12.6% vs. 7.2%).

Giredestrant treatment was well tolerated and considered to have comparable safety to PCET. Overall, 84.7% of giredestrant patients experienced at least one adverse event compared to 71.1% in patients treated with PCET. AEs leading to dose modification or interruption occurred in 13.3% of giredestrant patients and 8.6% of PCET patients. Few events led to treatment withdrawal, with 2 (1.3%) in the giredestrant arm and 3 (2%) in the PCET arm.

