3. SAMPLE SIZE DETERMINATION

The primary analysis of PFS will be conducted when approximately 166 PFS events from both arms are observed. The study is designed with 80% power at the 5% (two-sided) level of significance to detect hazard ratio of 0.647, which corresponds to an improvement in median PFS from 5.5 months to approximately 8.5 months. The largest hazard ratio (smallest effect size, minimal detectable difference, MDD) determined to be statistically significant at the 5% level will be approximately 0.738 (which corresponds to median improvement in PFS from 5.5 to 7.5 months).

Approximately 300 patients will be enrolled and randomized in a 1:1 ratio to receive either GDC-9545 (experimental arm) or physician's choice of endocrine monotherapy (control arm). Given assumptions on recruitment intensity (see [Table 2](#) below); the enrollment is projected to finish approximately 15 months after randomization of the first patient. For both the GDC-9545 and control arms, an annual loss to follow-up rate of 10% is assumed. On that basis, it is projected that the primary PFS analysis will occur approximately 18 months after the first patient is enrolled.

Table 2: Recruitment intensity

	Recruitment month from ramp-up to peak														
	1	2	3	4	5	6	7	8	9	10	11	12	13	14	15
Participants per month	1	4	9	14	19	23	26	29	28	29	28	29	28	29	4

Sample Size for the China Subpopulation

This study will initially enroll approximately 300 participants across all sites during the global enrollment phase. After completion of the global enrollment phase, additional participants may be enrolled in an extended China enrollment phase at sites in mainland China and/or Taiwan.

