5.4.1 Overall Survival

The secondary comparison of interest is the hazard ratio of Overall Survival (OS). The secondary trial objective is to demonstrate superiority of the GDC-9545 arm over the physician's choice of endocrine monotherapy treatment arm.

Following the estimand framework (ICH 2020), the attributes of the estimand for the secondary endpoint are defined as follows:

- **Population:** As defined for the primary estimand in section 5.3.1
- **Variable:** Overall Survival (OS), defined as time from randomization to death from any cause.
- **Treatment:** As defined for the primary estimand in section 5.3.1
- **Intercurrent events and Handling strategy**
 - Use of any non-protocol anti-cancer treatment (NPT) prior to disease progression as detailed in Protocol section 4.4.3. → Following treatment policy the ICE will be ignored and observations collected after the ICE will be used.
 - Discontinuation of study treatment prior to disease progression. → Following treatment policy the ICE will be ignored and observations collected after the ICE will be used.
- **Population-level summary:** Hazard ratio for OS.

As per protocol, crossover between treatment arms will not be permitted in the study hence crossover not anticipated as an ICE. If participants have any intercurrent events, then the strategies defined below to handle the intercurrent events will be implemented. Otherwise, data for patients who are alive at the time of the analysis data cutoff will be censored at the last date they were known to be alive. Data from patients without postbaseline information will be censored at the date of randomization plus 1 day.

OS will be hierarchically tested if the primary endpoint, PFS, is statistically significant at the primary PFS analysis. The OS analyses will be conducted at the time of the primary analysis of PFS, at least 12 months after the primary analysis, and at the end of the study, which is expected to occur at least 25 months after the last patient is enrolled in the global study, refer to section 5.8 for details on interim analysis for OS.

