5.4.2 Overall Response Rate

The analysis population for ORR will be full analysis set. Patients not meeting the criteria for ORR, including patients without any postbaseline tumor assessment, will be considered non-responders.

Following the estimand framework (ICH 2020), the attributes of the estimand for the secondary endpoint are defined as follows:

- **Population:** As defined for the primary estimand in section 5.3.1.
- **Variable:** ORR, defined as the proportion of patients with a CR or PR on two consecutive occasions ≥ 4 weeks apart, as determined by the investigator according to RECIST v1.1.
- **Treatment:** As defined for the primary estimand in section 5.3.1

- **Intercurrent events and Handling strategy:**
 - As described for the primary estimand in section 5.3.1.
 - **ICE Handling Strategy:**→ Following treatment policy, all the ICE's will be ignored and tumor assessment data collected after the ICE will be included in the ORR analysis.
- **Population-level summary:** Difference in proportion.

An estimate of ORR and 95% CI will be calculated using the Clopper-Pearson method for each treatment arm. ORR will be compared between treatment arms using the stratified Cochran-Mantel-Haenszel test. The stratification factors to be used will be the same as those used for the analysis of the primary endpoint. The difference in ORR between treatment arms will be calculated, and 95% CI will be calculated using the Newcombe methodology (Newcombe 1998).

5.4.3 **CBR**

Following the estimand framework (ICH 2020), the attributes of the estimand for the secondary endpoint are defined as follows:

- **Population:** As defined for the primary estimand in section 5.3.1
- **Variable:** CBR, defined as the proportion of patients with stable disease for ≥ 24 weeks or a CR or PR, as determined by the investigator according to RECIST v1.1.
- **Treatment:** As defined for the primary estimand in section 5.3.1
- **Intercurrent events and Handling strategy:**
 - As described for the primary estimand in section 5.3.1
 - **ICE Handling Strategy:**→ Following treatment policy, all the ICE's will be ignored and tumor assessment data collected after the ICE will be included in the CBR analysis.
- **Population-level summary:** Difference in proportion.

CBR analysis including handling of ICE will follow the same methods as those used for ORR.

5.4.4 **DOR**

Analysis of DOR will include only patients who had an objective response.

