5.8.1 Interim Analyses for Secondary Efficacy Endpoint: OS

The study will incorporate three OS analyses (two interim analyses and one final analysis). The first OS interim analysis will be performed at the time of the primary PFS analysis. The second OS interim analysis will be performed after the occurrence of approximately 119 deaths and is projected to occur at approximately 30 months (~12 months after Primary Analysis) after the first patient is randomized. The final OS analysis will be performed after the occurrence of approximately 149 deaths (projected to occur approximately ~40 months after the first patient is randomized). The Lan-DeMets implementation of the O'Brien and Fleming use function will be used to control the overall type I error for the OS comparison at a two-sided 0.05 significance level.

The OS analyses were designed with an overall 5% (two-sided) level of significance to detect HR ratio of 0.893, which corresponds to an improvement in median OS from 25 months to approximately 28 months. However, this study is not designed to formally test OS. For the target number of OS events and anticipated study timeline, the OS analyses will be largely underpowered, i.e. ~10% statistical power. The details of the OS analyses are shown in Table 3. The exact efficacy boundary will be updated based on the actual number of observed OS events at the time of OS analysis.

Table 3: Assumptions and Characteristics for the Interim and Final Analyses of OS

Assumption	Findings
First interim analysis of OS	
(to be performed at time of final PFS analysis)	
Estimated cutoff date ^a	18 months
Projected number of events (% of final events)	60 (20%)
Projected MDD ^b (p-value)	0.418 (< 0.0008)
Second interim analysis of OS	
Estimated cutoff date ^a	30 months
Projected number of events (% of final events)	119 (39.7%)
Projected MDD ^b (p-value)	0.661 (< 0.0242)
Final analysis of OS	
Estimated cutoff date ^a	40 months
Projected number of events (% of final events)	149 (49.7%)
Projected MDD ^b (p-value)	0.717 (< 0.0428)

HR = hazard ratio; MDD = minimally detectable difference;

^a Estimated data cutoff time from first randomization. Analysis results will be available after data cleaning.

^b The largest observed HR that is projected to be statistically significant.

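### CBR inherits the ORR non-responder rule with no minimum follow-up, so on the planned timeline about 48 of 300 patients cannot qualify through stable disease; the reported rates are modestly lowered in both arms

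*SAP*

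**What the plan says.** SAP 5.4.3 defines CBR as the proportion of patients with stable disease lasting at least 24 weeks, or with a CR or PR, by investigator assessment. For the method it says only: "CBR analysis including handling of ICE will follow the same methods as those used for ORR". SAP 5.4.2 sets the ORR population as the full analysis set, and patients who do not meet the criteria, "including patients without any postbaseline tumor assessment, will be considered non-responders". Protocol 6.4.2.4 also sends CBR to the ORR methods. Neither document gives a minimum follow-up for CBR, or a rule for a patient whose stable disease is ongoing but shorter than 24 weeks at the cutoff.

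On timing, SAP section 3 projects enrolment to finish at about month 15, and "it is projected that the primary PFS analysis will occur approximately 18 months after the first patient is enrolled". The second OS interim analysis "is projected to occur at approximately 30 months" from first randomisation; SAP 5.4.1 places that analysis "at least 12 months after the primary analysis". No CBR analysis is specified at that later cut.

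Protocol 1.2.2.2 reports results at the primary cutoff: CBR 31.8% (giredestrant) vs 21.1% (control), ORR 12.6% vs 7.2%, 303 patients enrolled. It adds that "median duration of follow-up was 7.89 months" and that "15.2% patients had discontinued from the study".

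**The concern.** The non-responder rule suits ORR reasonably well, because a response can appear at the first or second scan. It suits CBR less well, because one route to success has a fixed 24-week time requirement. A patient randomised less than 24 weeks before the cutoff cannot take that route, whatever the disease does. PFS and DOR deal with incomplete follow-up by censoring; CBR has no counterpart.

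The CBR estimate therefore depends on accrual speed and cutoff date as well as on treatment. Both arms are lowered and, if the drug works, the difference between them shrinks towards zero. What is at stake is the level of a secondary endpoint and its comparability across data cuts. CBR is outside the PFS-then-OS testing hierarchy in SAP 2.1.

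**Working it through.** **Plan's own figures.** Events for 80% power at HR 0.647, two-sided 5%: 4 × (1.960 + 0.842)² / (ln 0.647)² = 165.6, i.e. 166 as stated. SAP Table 2 (1, 4, 9, 14, 19, 23, 26, 29, 28, 29, 28, 29, 28, 29, 4 per month) sums to 300. With exponential PFS (medians 5.5 and 8.5 months) and 10% annual loss, that accrual gives about 170 events at month 18. The month-18 cutoff is thus consistent with the plan's inputs.

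**Patients exposed.** 24 weeks = 168 / 30.44 = 5.52 months, and 18 − 5.52 = 12.48. Enrolled after month 12.48: 0.52 × 28 + 29 + 4 = 47.5, which is 15.8% of 300. The count depends on the cutoff: 61.6 at month 17.5, 19.1 at month 19, 0 at month 30.

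**Was everyone in the reported denominator?** Searching arm sizes from 100 to 159, 31.8% together with 12.6% fits only N = 151 (48 and 19 patients), and 21.1% with 7.2% fits only N = 152 (32 and 11). 151 + 152 = 303, all enrolled, so nobody was excluded for short follow-up.

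**Misclassified, planning medians.** P(PFS > 24 weeks) = exp(−ln 2 × 5.52 / median) = 0.499 (control) and 0.638 (GDC-9545). Progression-free among the late patients: 23.8 × (0.499 + 0.638) = 27.0. This includes responders, who already count as clinical benefit. All the late patients have passed week 8 and about 45 have reached week 16, so most responses could have been seen. Crediting responses at the reported ORRs removes 23.8 × (0.072 + 0.126) = 4.7, leaving about 22. CBR moves from 49.9% vs 63.8% (13.9 points) to 43.1% vs 55.6% (12.5 points).

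**Misclassified, reported rates.** With late share f = 0.1585:

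| | Control | GDC-9545 | Difference | Misclassified of 303 |
|---|---|---|---|---|
| Reported | 21.1% | 31.8% | 10.7 | – |
| Responses credited: (obs − f × ORR)/(1 − f) | 23.7% | 35.4% | 11.8 | 9.4 |
| No response credited: obs/(1 − f) | 25.0% | 37.8% | 12.8 | 15.1 |

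**Precision.** The 95% half-width for the difference is 1.96 × √[Σ p(1 − p)/n]. It is 11.1 points at the planning rates (150 per arm) and 9.9 points at the reported rates (152 and 151).

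**Actual late share.** Median entry under Table 2 is month 8.89, so median potential follow-up at month 18 is 9.1 months, against 7.89 reported. Depending on how follow-up was defined, 7.89 is compatible with a late share of about 8-28% for accrual lasting 10-15 months, and 4-12% for 9 months. The same back-calculation gives about 2-4 patients at a 4.2% share and 19-30 at 27.5% (lower figure with responses credited, upper without).

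**The case against.** - **The planning-median figure is out of line with the data.** Exponential PFS with those medians predicts CBRs of about 50% and 64%, far above the 21.1% and 31.8% reported. This stands: 22 is an upper figure under the design assumptions, and the 9 from the trial's own rates is better anchored.
- **The late share is not documented.** Accrual dates and the definition of follow-up are not given. This also stands: the counts are conditional on 15.8% and do not bound the true number.
- **The rule was pre-specified, is identical in both arms, and PFS Kaplan-Meier curves are already planned.** Progression-free probability at 24 weeks can be read from those curves without failing late entrants. This lowers the importance of the point. It does not correct the CBR, which is reported as its own endpoint and is not the same quantity.

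Two stronger readings are tempting. A reader might infer that 27 patients were wrongly failed; that figure counts responders, whom the CBR definition already accepts. A reader might also infer that the treatment comparison is invalid or that the trial's conclusion is affected. The documents support neither. Randomisation spreads late entry evenly over the arms in expectation, so with no treatment effect the expected difference stays at zero, and the primary PFS analysis does not use this rule.

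**Conclusion.** The point holds, at minor severity. The rule and the planned 48 of 300 follow directly from the SAP. With responses credited, about 9 to 22 patients are scored as failures because of the calendar, conditional on a 15.8% late share. At that share the reported rates would be roughly 24-25% vs 35-38%, and the difference would rise by 1 to 2 points against a half-width of 10 to 11. No conclusion changes.

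Assumptions: uniform accrual within each month; late entrants have the same underlying rates as earlier ones; responses among them are credited at the reported ORRs; exponential PFS for the planning case only; loss to follow-up ignored in the misclassification counts.

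**What to change.** Keep the full-set CBR as reported. Add to SAP 5.4.3 one further CBR on all randomised patients at the second OS data cut (about month 30). Since that cut comes at least 12 months after the primary analysis, every patient in the global population will then have more than 24 weeks of potential follow-up, whatever the actual accrual. Because CBR from this open-label trial has already been reported, label the addition supplementary and post hoc; it must not replace the reported result.

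The cost is one table plus extraction of tumour assessments at a cut now planned for OS. No new visits are needed, since Protocol 4.5.6.2 already continues scans until progression.

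If the sponsor prefers to restrict by randomisation date at the primary cutoff, requiring 25 weeks (24 plus the 7-day window) drops 0.75 × 28 + 33 = 54 of the 300 planned patients. The SAP must then also state how a week-24 scan done up to 7 days early counts. A patient scanned at week 23 has not documented 24 weeks and is next due at about week 32, so could still fail only because of the cutoff.

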5.4.5 PFS by ESR1 Mutation Status

The analysis population for PFS by ESR1 mutation will be all randomized patients with evaluable plasma ctDNA at baseline.

Following the estimand framework introduced in the ICH-E9 addendum ([ICH 2020](#)), the attributes of the estimand for the secondary endpoint are defined as follows:

- **Population:** All randomized patients with evaluable plasma ctDNA at baseline.
- **Variable:** Investigator-assessed PFS in subgroups categorized by ESR1 mutation status determined at baseline from plasma ctDNA.
- **Treatment:** As defined for the primary estimand in section [5.3.1](#)
- **Intercurrent events and Handling strategy**
 - As described for the primary estimand in section [5.3.1](#).
 - **ICE Handling Strategy:**→ Following treatment policy, the above ICE will be ignored and tumor assessment data collected after the ICE will be included in the analysis.
- **Population-level summary:** Hazard ratio.

PFS by ESR1 mutation status (mutation detected, no mutation detected) will be compared between treatment arms using the stratified log-rank test. Analytical approach and handling of ICE will follow the same methods as those used for PFS in section [5.3.2](#).

5.4.6 Patient Reported Outcomes

The secondary efficacy objective of the study is based on the following Patient Reported Outcome (PRO) endpoints:

- **Time to deterioration (TTD) in pain severity after randomization**, defined as the time from randomization to the first documentation of a ≥ 2 -point increase from baseline on the "worst pain" item score from the Brief Pain Inventory–Short Form (BPI-SF)
- **TTD in pain presence and interference after randomization**, defined as the time from randomization to the first documentation of a ≥ 10 -point increase from baseline in the European Organisation for Research and Treatment of Cancer (EORTC) QLQ-C30 linearly transformed pain scale score
- **TTD in Physical Functioning (PF) after randomization**, defined as the time from randomization to the first documentation of a ≥ 10 -point decrease from baseline in the EORTC QLQ-C30 linearly transformed PF scale score
- **TTD in Role Functioning (RF) after randomization**, defined as the time from randomization to the first documentation of a ≥ 10 -point decrease from baseline in the EORTC QLQ-C30 linearly transformed RF scale score
- **TTD in global health status (GHS) and quality of life (QoL) after randomization**, defined as the time from randomization to the first documentation of a ≥ 10 -point decrease from baseline in the EORTC QLQ-C30 linearly transformed GHS/QoL scale score

All randomized patients will be used for completion analyses and time-to-deterioration (TTD) analyses. Analyses will be performed based on the treatment arm assigned at randomization. The comparison of interest is the difference in time to deterioration between treatment arms expressed by the hazard ratio. The Kaplan-Meier analysis methods similar to those described for PFS analysis will be applied for TTD analysis. Patients who do not have an observed deterioration prior to discontinuation from study treatment or at the time of the clinical cut-off date (CCOD), will be censored at the last available assessment date prior to or at the time of discontinuation from study treatment or CCOD, whatever is earlier. Data for patients without a post baseline assessment will be censored at the time of randomization plus 1 day.

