Patients will be followed for safety for 30 days after the final dose of study treatment, including a treatment discontinuation visit at 30 days after the final dose (unless final dose resulted in a dose delay prior to decision to discontinue). For the control arm, the upper limit of the visit window will be dependent upon maximum dosing delay as permitted per local guidelines. Thereafter, information on survival and new anti-cancer therapy will be collected every 6 months until death (unless the patient withdraws consent or the Sponsor terminates the study). The survival follow-up period for patients remaining in the study will conclude at the time of the final OS analysis.

After the date of randomization, tumor assessments will be performed every 8 weeks for the first 18 months, then every 12 weeks thereafter, with the

exception of bone scans, which will be performed every 24 weeks or as clinically indicated (see Section [4.5.6.2](#) for detailed information).

Efficacy analyses will be based on the local radiologist's or investigator's tumor assessments. Radiographic images, photographs, and clinical information will be sent to a blinded, independent core imaging laboratory to enable a retrospective evaluation of disease response and progression by an Independent Review Committee (IRC) (see Section [3.1.2](#)).

To evaluate the PK properties of GDC-9545, sparse PK samples will be collected at various timepoints before and after dosing from all patients in the GDC-9545 arm; a subset of patients in the GDC-9545 arm will be enrolled for intensive GDC-9545 PK sampling (see [Appendix 2](#)).

[figure not shown]
Patient-reported outcome (PRO) instruments will be completed by patients to evaluate the treatment impact from the patient's perspective.

Optional patient interviews will be performed among a subset (up to 30) of patients receiving GDC-9545, to explore patients' experience of study drug, therapeutic context, and disease journey.

All patients will be closely monitored for adverse events throughout the study, and adverse events will be graded according to NCI CTCAE v5.0. An IMC will also provide safety oversight as outlined in Section [3.1.3](#).

[Figure 1](#) presents an overview of the study design. A schedule of activities is provided in [Appendix 1](#).

Figure 1 Study Schema

ER=estrogen receptor; HER2=human epidermal growth factor receptor 2; LHRH=luteinizing hormone-releasing hormone; PO=orally; QD=once a day; R=randomization.

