6.4.2.6 Patient-Reported Outcomes

The PRO-evaluable population consists of randomized patients with at least one postbaseline assessment. Data for patients who do not have an observed deterioration at the time of the CCOD will be censored at the last non-missing assessment date. Data for patients without a postbaseline assessment will be censored at the time of randomization plus 1 day.

To evaluate TTD in pain severity, the "worst pain" item from the BPI-SF will be assessed. A 2-point change in the worst pain rating is defined as clinically meaningful (Mathias et al. 2010).

TTD in EORTC QLQ-C30 scale scores for pain presence and interference (Items 9 and 19), PF (Items 1–5), RF (Items 6 and 7), and GHS/ QoL (Items 29 and 30) will be assessed. A ≥ 10 -point change in EORTC QLQ-C30 scale scores is defined as clinically meaningful (Osoba et al. 1998).

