5.3.1 Definition of Primary Estimand

Following the estimand framework introduced in the ICH-E9 addendum ([ICH 2020](#)), the attributes of the estimand built around the primary endpoint are defined as follows:

- **Population:** Patients with previously treated estrogen receptor (ER)-positive, HER2-negative locally advanced or metastatic breast cancer who have received one or two prior lines of systemic therapy in the locally advanced or metastatic setting, as defined by the inclusion / exclusion criteria in study protocol (refer to Protocol section 4.1)
- **Variable:** Progression Free Survival (PFS), defined as time after randomization to the first occurrence of disease progression or death from any cause (whichever occurs first), as determined by the investigator according to RECIST v1.1
- **Treatment:** GDC-9545 or physician's choice of endocrine monotherapy. During the conduct of the study, participants may also receive concomitant medications as detailed in Protocol section 4.4.

- **Intercurrent events and Handling Strategy:**
 - Use of any non-protocol anti-cancer treatment (NPT) prior to disease progression as detailed in Protocol section 4.4.3. → Following treatment policy the ICE will be ignored and tumor assessment data collected after the ICE will be included in the PFS analysis
 - Discontinuation of study treatment prior to disease progression → Following treatment policy the ICE will be ignored and tumor assessment data collected after the ICE will be included in the PFS analysis.
- **Population-level summary:** Hazard ratio

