5.4 SECONDARY ENDPOINTS ANALYSES

The secondary efficacy endpoints for this study Overall Survival (OS), Objective response rate (ORR), Duration of response (DOR), Clinical Benefit Rate (CBR) and PFS in subgroups characterized by baseline ESR1 mutation status and the PROs Time to deterioration (TTD) in pain severity, pain presence/interference, physical functioning, role functioning, global health status and quality of life, are defined in Protocol Section 2.1.2. The subset of corresponding secondary efficacy endpoints which are not derived from patient-reported outcome (PRO) measures, are expressed using the estimand framework. Analysis method for all the secondary endpoints are described in following sub-section.

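### SAP 5.4.6 stops all five patient-reported time-to-deterioration endpoints at an undated treatment discontinuation, treats a deterioration recorded at that point in two ways, and keeps no all-data analysis

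*SAP*

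**What the plan says.** SAP 5.4.6 analyses TTD in all randomized patients by assigned arm, with the hazard ratio as the summary. Its event clause treats as event-free those who "do not have an observed deterioration prior to discontinuation from study treatment" or by the CCOD. Its censoring clause then has them "censored at the last available assessment date prior to or at the time of discontinuation from study treatment", or at the CCOD if that comes first.

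Protocol 6.4.2.6 makes no reference to treatment. Patients with no deterioration by the CCOD "will be censored at the last non-missing assessment date". SAP 5 says that the SAP supersedes the protocol's analyses.

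SAP 5.4 uses estimands only for the secondary endpoints "which are not derived from patient-reported outcome (PRO) measures, are expressed using the estimand framework", so TTD has no stated intercurrent-event strategy. SAP 5.3.5 restricts supplementary estimand analyses to investigator-assessed PFS.

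Protocol Appendix 1 schedules questionnaires at the treatment discontinuation visit and 90 days after discontinuation. The 90-day visit covers all five TTD scales. Patients who stop without progression continue on the tumor-assessment schedule instead.

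Protocol 4.6.1 places the discontinuation visit 30 (+3) days after the final dose. It lets a progression visit stand in if that falls within 28 (+3) days of the final dose, and it ties the control arm's upper window to local dosing-delay rules. Protocol 3.1.1 separates the final dose from the decision to stop: "unless final dose resulted in a dose delay prior to decision to discontinue".

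**The concern.** The rule cannot be programmed in only one way. The discontinuation date has several candidates, and the two clauses give different answers for a score recorded on it. Two programmers could report different event counts from the same data.

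The cut-off also falls where deterioration is most likely to appear. Protocol 4.6.1 requires stopping at progression (apart from isolated brain metastases) and at symptomatic deterioration attributed to progression. Protocol 3.3.6 expects progression to bring more pain. Censoring at that moment is plausibly related to the outcome and can overstate deterioration-free time. The later questionnaires that would show this are scheduled but do not enter TTD, and no second analysis uses them.

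**Working it through.** **Step 1: the clauses side by side.** Take a patient whose first qualifying score is recorded at discontinuation.

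- SAP event clause: the deterioration was not seen before discontinuation, so there is no event.
- SAP censoring clause: that assessment lies inside the window, so the patient is censored on the date the deterioration was recorded.
- The endpoint definition in the same section (time to first documentation) and protocol 6.4.2.6: an event on that date.

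**Step 2: the candidate dates.** Assume a progression scan on day 112. A daily oral drug is last taken that day. A monthly injection was last given on day 112 − 28 = 84, and the next one is withheld. Fulvestrant is a control option (protocol 4.3.1.2) and is described as monthly in protocol 1.2.1.

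| Reading of discontinuation | Daily oral | Monthly injection |
|---|---|---|
| Final dose | 112 | 84 |
| Progression visit used as the discontinuation visit | 112 | 112 |
| Separate visit, final dose + 30 days | 142 | 114 |

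The substitution is allowed in both columns, because 0 and 28 days are within 28 (+3). For the same disease course the columns differ by 28, 0 and 28 days.

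**Step 3: how many patients the cut-off reaches.** Protocol 1.2.2.2 reports 303 enrolled at the primary CCOD and 15.2% off study (about 46). Of the other 257, "the majority of those remaining had discontinued treatment", which means at least 129. If patients who left the study are also off treatment, at least 46 + 129 = 175 of 303 (58%) had stopped. Adverse-event withdrawal was rare: "Few events led to treatment withdrawal, with 2 (1.3%) in the giredestrant arm and 3 (2%) in the PCET arm". Most stopping therefore probably followed progression.

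**Step 4: size.** The plan gives no TTD event count or power, so there is no figure to reproduce. The design inputs used below do reproduce: 4(1.960 + 0.842)²/(ln 0.647)² = 166 PFS events, and the accrual in SAP Table 2 sums to 300.

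Simulation A (6,000 patients per scenario, scaled to 300) used:

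- SAP Table 2 accrual, an 18-month cut-off, and PFS medians of 5.5 and 8.5 months;
- 8-weekly scans, with stopping at the progression scan;
- PROs at days 28, 56, 112 and every 56 days while on treatment, then at final dose + 30 days and 90 days after that;
- assumed median time to deterioration before progression of 12 or 24 months, with the hazard multiplied by 1, 3 or 6 after progression.

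| Rule | Daily oral in both arms: events; HR | Whole control arm on monthly injection: events; HR |
|---|---|---|
| Protocol 6.4.2.6 | 56–167; 0.85–0.96 | 58–164; 0.83–0.91 |
| SAP, cut at final dose | 46–113 (18%–41% lost); 0.90–0.98 | 44–94 (24%–50% lost); 0.89–1.22 |
| SAP, cut at visit, visit counts | 49–139 (12.5%–24% lost); 0.87–0.95 | 51–127 (12%–29% lost); 0.96–1.08 |
| SAP, cut at visit, read literally (no event, censored that day) | 46–113; 0.90–0.98 | 44–94; 1.08–1.47 |

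The Monte Carlo standard error of each hazard ratio is about 0.04–0.07.

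Simulation B (200,000 patients per arm) used the same dosing pattern in both arms, deterioration hazards of 0.03 or 0.06 per month, a 1-, 2- or 4-fold rise from one month before progression, PFS HR 0.647 or 0.81, and 10% annual loss to follow-up.

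| Cut-off | Events lost, visit not counted | Events lost, visit counted | HR shift, not counted | HR shift, counted |
|---|---|---|---|---|
| 18 months | 16%–58% | 9%–29% | up to 0.13 | within 0.03 |
| 40 months | 19%–62% | 12%–36% | up to 0.15 | within about 0.03 |

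At 18 months with a 2- or 4-fold rise, the 12-month deterioration-free proportion exceeds the protocol-rule value by 5–25 points (visit not counted) or 2–10 points (counted).

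Two further checks put the whole control arm on monthly injections and counted the visit. The TTD hazard ratio moved by about 0.01–0.11 in one and 0.1–0.18 in the other, passing 1 in some scenarios. With oral control it moved by about 0.02 or less.

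**The case against.** Much of the other side stands. The SAP may override the protocol, so the difference between them is not an error in itself. An on-treatment rule is defensible: protocol 4.4.3 warns that palliative radiotherapy may alter TTD in pain. Only the date is open, not the concept, and the endpoint definition favours counting a deterioration recorded at the boundary. SAP 5.5 still summarises scores at each assessment time point without a discontinuation cut-off, so later questionnaires are left out of TTD only. TTD lies outside the PFS-then-OS hierarchy of SAP 2.1, and PFS has already been analysed and was not met.

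The loss figures are measured against a protocol rule that is itself imperfect. In Simulation B its 12-month estimate differed from the assumed truth by −4 to +6 points at 18 months and 0 to +8 points at 40 months, because patients who progress leave PRO follow-up after the 90-day visit. Missing questionnaires also shrink the loss. Assuming that half the 90-day visits are missed cut it from 11% to 6% in one case and from 18% to 10% in another.

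A reader might infer that the SAP contradicts its own treatment-policy approach to PFS. The documents do not support that in general. The intercurrent event there is "Discontinuation of study treatment prior to disease progression", so the parallel is exact only for stopping before progression, and the one such figure given is the small adverse-event count above.

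These points limit the concern. They do not supply a date, reconcile the two clauses or provide an all-data TTD analysis.

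**Conclusion.** The point holds as a defect of specification and a missing companion analysis. The cut-off date is not stated, the clauses conflict on a score recorded at it, and the protocol's all-data rule is dropped from TTD. The SAP text available gives no reason, although its front matter could not be checked.

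Event loss is roughly 10% to 60% of protocol-rule events. That range rests on assumed deterioration rates, near-complete questionnaires and the reading chosen.

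A reader might infer that the distortion runs toward the null, or that it is negligible once the discontinuation visit counts. Neither is established. Both hold only when the arms share a dosing pattern. With a monthly injection as control the cut-off falls at a different time relative to progression in each arm, and the hazard ratio can cross 1. An all-injection control arm is an extreme case, and the documents do not give the fulvestrant share.

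The primary result and type I error are unaffected. Severity is minor to should-fix.

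**What to change.** In SAP 5.4.6:

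1. Add, alongside the existing rule, a treatment-policy TTD analysis under protocol 6.4.2.6. It uses all post-baseline PROs on or before the CCOD, including the discontinuation visit, the 90-day visit and later scheduled assessments. Event-free patients are censored at the last non-missing assessment. Label it as added after the primary results were known.
2. Keep the existing rule and name it the on-treatment analysis. State one cut-off date, defined the same way in both arms, that does not depend on a site's choice of visit or on local dosing-delay windows. The recorded date of the decision to stop is a candidate if the eCRF holds it. The final dose date is uniform in wording but not in effect when one arm is injected monthly.
3. State that a deterioration first recorded on or before that cut-off, or on or before the CCOD if earlier, is an event on the date it was recorded. Censor all other patients at the last non-missing assessment on or before the same limit.

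The cost is a wording change and one extra run on questionnaires already scheduled. There are two downsides. Some later scores will reflect subsequent therapy or radiotherapy, and dependent censoring remains after the 90-day visit for patients who progressed.
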